### **5.3 Randomization and Treatment Delivery.**

Following completion of the baseline survey, participants will be randomized to the immediate start resiliency intervention group (IG) or waitlist control group (WG). Randomization will be conducted using a random plan generator. Groups will consist of up to approximately 8 participants. We will run approximately 6 or more separate intervention and waitlist control groups, for a total of 72 survivors. [name], a psychology trainee in the BMED internship program, or a pre-doctoral medical student, all under the supervision of [name] as study staff, will lead the group sessions, some of which will be audio-recorded for fidelity. Medical students will not under any circumstances conduct consent in their role as study staff. Prior to running the groups, [name] will train study staff on the study protocol, and we will have weekly supervision meetings to provide feedback and ensure fidelity. To decrease participant burden and extend reach, both groups will be delivered via MGH Telehealth (as successfully done in our sister protocols: DF/HCC #17-063 & DF/HCC #17-315).

### **5.4 Description of the Interventions.**

**5.4.1 3RP-AYA treatment:** Similar to our sister protocol (DF/HCC #17-063), and slightly adapted based on findings from our focus groups with AYAs (DF/HCC #17-315) The 3RP-AYA will be delivered in weekly sessions over the course of approximately 8 weeks, for a total of 8 sessions, which are approximately 90 minutes each. Modeled after the central tenets of the 3RP, each session includes repetition of core components, which include: 1) 10-point analogue scales of stress, distress, and coping (resembles distress thermometer), 2) weekly goal check-ins, 3) RR-practice, and 4) mini relaxation practice. Participants will learn a new RR strategy at each session that will be based on identified mind-body interests, maximizing the likelihood of finding a technique that is helpful for them. Throughout treatment, participants will be encouraged to practice RR strategies at home for at least 10-20 minutes each day, and they will be asked to document the frequency and duration of practice in weekly practice logs (Appendix 8.27) to record RR adherence. Participants will receive the 3RP-AYA patient manual, which describes the content of the 3RP sessions, and RR-based guided meditation audio files to help them elicit the RR at home each day. The audio files that guide the subject through the procedures have been used in other clinical research studies and clinical practice. It introduces a relaxation sequence to help participants elicit the RR, including some of the key elements such as breath awareness, body scan and use of a focus word, while instructing the participant to

passively ignore intrusive thoughts. Additional treatment components based on the 3RP model (Figure 1) and identified qualitative interview themes (DF/HCC #17-315) include coping logs that provide examples drawn from common transitional challenges identified by survivors (e.g., starting/graduating college; getting follow-up scans), which will facilitate discussion and practice of restructuring and positive reframing techniques. Lastly, social and educational topics identified in our sister protocol (DF/HCC #17-315), such as how to tell friends about their cancer experience, having empathy for “small things” and relating to others post-cancer treatment, preparing for high school/college, and managing parents’ anxieties, will be interwoven throughout the program and used to guide survivors in applying learned skills (e.g., identifying types of social support needed and developing strategies to facilitate social outreach and connection). We will also collect total number and timing of sessions per participant. The topics addressed in each of the eight 3RP sessions are described in Appendix 8.18. In order to remain transparent during the study and give back to those willing to participate, participants will be offered the chance to have a brief conversation with the study PI, [name], at a future date by filling out a Results Reporting Form (Appendix 8.26). Participants will be given this form after they have completed the intervention and will be told of the results after preliminary study results are available.

**5.4.2 Immediate start intervention group (IG).** The immediate start group will receive the intervention immediately after completing the baseline assessment (T0), and they will complete a post-treatment questionnaire (T1) to examine pre-post treatment changes in exploratory measures. Completion of T2 measures will allow for us to examine potential maintenance of intervention benefits (by evaluating change in scores from T1 to T2) within the intervention group only.

**5.4.3 Waitlist Control Group.** The waitlist control design allows all participants who enroll in this study the opportunity to get the 3RP-AYA. Participants in the Waitlist Control Group will be enrolled and complete baseline at the same time as the 3RP Intervention Group, and they will will complete the baseline a second time after the immediate start group completes the 3RP-AYA to allow for pre-post treatment group comparisons (T0 vs T1). The waitlist control group will also complete an assessment after receiving the 3RP-AYA treatment to examine pre-post treatment changes in exploratory measures (T1-T2).

## 5.5 Data Collection and Storage.

Prior to study enrollment, study data will be collected via medical record review for Partners patients or through patient self-report, if no available EMR through the Partners Healthcare System, at screening to determine study eligibility. In addition, we will gather descriptive information about our sample via brief surveys and assess levels of the stress hormone cortisol via hair sample collection. Specifically, we will collect data on:

Data	At Screening	At Baseline	At 3RP	At Post-3RP	At 3-Month Follow-Up
Date of birth	x				
Gender	x				
Languages spoken	x				
Cancer diagnosis	x				
Date of diagnosis	x				
Treatment type(s)	x				
Date of treatment completion	x				

Data	At Screening	At Baseline	At 3RP	At Post-3RP	At 3-Month Follow-Up
Demographic factors		x			
Psychosocial measures:					
Visual Analog Scales		x		x	x
Intolerance of Uncertainty Scale		x		x	x
Measure of Current Status – Part A (MOCS-A)		x		x	x
Patient-Reported Outcomes Measurement Information System (PROMIS) Measures		x		x	x
Coping Self-efficacy Scale		x		x	x
Health Behavior Questions		x		x	x
Penn State Worry Questionnaire (PSW-Q)		x		x	x
Interpersonal Reactivity Index		x		x	x
Current Experiences Scale (CES)		x		x	x
Hair cortisol measurement		x		x	
3RP acceptability questionnaire				x (intervention arm only)	x (waitlist arm only)
Weekly RR practice logs (Appendix 8.27)			x		
COVID19 Supplementary Questions		x		x	x
Optional Exit Interview (Appendix 8.29)					x (after completion of all study measures)

To safeguard participant information and confidentiality, all data will be stored in locked cabinets at MGH and/or in password-protected computer files, accessible only to trained and IRB-approved study staff. Source documents completed by participants will be scanned and stored electronically as detailed in Section 4.2b of this protocol. Participants' data will be identified by an ID number only, and a link between names and ID numbers will be kept separately under lock and key or in a separate password protected document accessible only by study staff. Data identified by ID numbers (de-identified) may also be stored in REDCap, a secure, web-based application designed to support data capture for research studies. Audio-recordings of the exit interviews and expert interviews will be uploaded to our study access-restricted drive. In efforts to remain compliant with NIH guidelines for scientific record keeping, audio recordings will be retained for at least two years after the study has ended. After that point, the recordings will be deleted and only de-identified

transcripts will be stored on our secure study-access restricted drive to preserve patient anonymity. Audio files will be sent securely and transcribed by transcribeme.com. Transcripts of all interviews will be de-identified, and participants will be directed to avoid using personal identifiers (i.e., birthdays, home address, full names) during the course of the interview, thus maintaining patient anonymity and confidentiality during the interview.

**5.51. Handling of Study Documents.** Study source documents, including but not limited to signed informed consent forms, completed eligibility checklists, and participant questionnaires, will be scanned and stored digitally as certified copies on a secure drive only available for access to trained study staff working with the documents. The drive will be only accessible with proper invitation to the drive by the Principle Investigator through their Partners account, which will require personal username and password information to access. Trained study staff will follow specific standard operating procedures for handling source documents and certifying each copy appropriately. The procedures are as follows. After source documentation is filled out by the participant, study staff will collect the original source document. The study staff member scanning documents will be kept as consistent as possible throughout the duration of the study to ensure uniformity among source documentation handling. Location, time, and date of the scanning of the document will be recorded at the time of scanning. Study staff will fill out the Source Documentation Certified Copy Cover Sheet (Appendix 8.23) and include this as the first page of the electronic version of the source document. After the source document is scanned and the corresponding electronic document is confirmed to be legible, all facing the correct direction, and together as a single document, it will be collected and destroyed immediately. Study staff will destroy the original copy of the source document by following MGH procedures of destroying documents with Personal Health Information (PHI). Electronic versions of source documents will allow study staff to access these documents regardless of where the original copy is stored, which may be inconvenient, increase study staff burden, and study cost if storage of documents is far from the location where research activities will be conducted or required to be placed in long term storage. Electronic copies of these documents will eliminate the need for space concerns and cost of storage.

## 5.6 Description of Study Process

**5.6.1 Instrument Administration:** The Baseline (Timepoint 0), Post-3RP (Timeline 1), and 3-month Follow-up (Timeline 2) Questionnaires will be self-administered by participants either on paper or electronically via REDCap survey in accordance with patient preferences. Patients may also elect to complete the questionnaires at home and mail them back to the study staff in a stamped, pre-addressed envelope, or complete them with a member of study staff over the phone, via secure videoconferencing, or in clinic. Patients may be recruited for the study and enrolled when they become available for an upcoming intervention or WCG session in the future. As outlined in Section 4.4, participants will not be registered on the study until they complete the baseline questionnaire and are randomized. The Timepoint 1 (Post-3RP data collection for the intervention group and baseline data collection for the WCG) may be completed up to approximately 12 weeks (+/- 2 weeks) after Timepoint 0, and Timepoint 2 (Follow-up data collection for the intervention group and Post-3RP data collection for the WCG) may be completed approximately 24-weeks (+/- 2 weeks) after Timepoint 0.

**5.6.2 Hair Cortisol:** Similar to other studies which have utilized hair sample collection for cortisol measurement (Partners IRB Protocol#: 2016P001622; DF/HCC #17-063), participants will be asked to cut a small amount of hair (approximately 150 strands, which is about the diameter of a pencil eraser) as close to the scalp as possible (about 3 cm), and from the back of their head. They will be asked to band or tie the strands near the scalp end, place on the sample in aluminum foil, and return in an envelope to MGH. Participants will be sent detailed sampling instructions (Appendix 8.16) and stamped, addressed envelopes to facilitate mailing. Study staff will explain the purpose of hair collection to participants to facilitate transparency of the study and invite participants the opportunity to learn more about their stress levels. A member of study staff will review the sampling procedures in detail with participants either in-person at MGH or during the brief test call, according to patient preferences and availability. Participants will be asked to provide hair samples at Timepoints 0 and 1. Participants will also be provided with the Hair Cortisol Results

Form (Appendix 8.19), which will give participants the option to receive the results of their hair cortisol levels via a phone or secure videoconferencing conversation with the study PI, which will be scheduled after the completion of all study activities.

**5.6.3 Intervention Administration:** The 3RP-AYA will be administered virtually via Partners Telehealth videoconferencing software by the PI or by a member of the study team who has doctoral-level training in clinical psychology or medicine and is experienced in conducting the 3RP (e.g. clinical psychologists, fellows, post-docs). The 3RP-AYA consists of eight, 90-minute weekly RR-training group sessions conducted over the course of approximately 8 weeks, and there will be up to approximately 8 participants per group. The topics addressed in the eight 3RP-AYA sessions are listed in Appendix 8.18. As described in protocol section 4.2, in order to facilitate proficiency with the Telemedicine software, participants may test the software with a study staff member during a brief test call prior to the start of the intervention.

**5.6.4 Special Concerns:** Some participants may feel uncomfortable sending us a hair sample; participants will not be required to participate in the hair sample collection if they feel uncomfortable or are otherwise unable to provide a hair sample. Participants can still remain in the study if they do not wish to complete a hair cortisol sample. Additionally, some subjects may not wish to participate in the qualitative exit interview for the study; this component of the study will also be considered optional.

**5.6.5 Compensation:** Subjects will receive \$10 in remuneration for completion of the baseline survey, and \$20 in remuneration for completion of the post-3RP survey, and \$25 for completion of the follow-up survey (up to \$55 total). Participants will receive \$15 and \$20 in remuneration for completion of the baseline and follow-up hair sample(s), respectively (up to \$35 total). Participants who complete the optional exit interview may receive \$30. In total, participants may earn up to \$120 throughout the duration of their entire participation. As required for compliance with Partners Healthcare remuneration policy, we will collect participants' contact information (see Remuneration Form in Appendix 8.20). If a participant is unable to provide a Social Security Number (SSN) or Individual Taxpayer Identification Number (ITIN) because of their citizenship status (e.g. non-US citizen), they will receive an eCheck or equivalent gift card payment for study participation, as per their preference. This gift card will be sent to them electronically or in the mail, as per the participant's preference. Gift card payment information will be documented to ensure that the participant has received the appropriate payment.

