## 4.2 The Informed Consent Process & Enrollment

A member of the study staff will determine patients' eligibility status, explain the purpose of the study and study procedures, and answer any questions prior to completing informed consent. During the informed consent discussion, study staff will carefully review the informed consent document with the patient.

All patients will be provided with study staff contact information if any questions or concerns regarding the research arise. In addition, all patients will be explicitly informed that Partners Telehealth services provides

secure HIPAA-compliant videoconferencing software. We will explain that although we will do our best to ensure confidentiality on our end, we cannot guarantee 100% that other group members will not share the content of the group. Patients will also be advised to wear headphones and sit in a quiet place during the virtual study visits to protect their own, and other group members', privacy. Participants will also be informed that after signing the informed consent, they will complete a brief test call with a study staff member using the videoconferencing software in order to ensure proficiency with the software. If a participant completes a study questionnaire and is later deemed ineligible, their responses will be exempt from data analysis. Subjects who are found to be unable to use the videoconferencing software during the brief test call will be considered ineligible for the study.

For eligible patients, a trained member of study staff with a bachelor's-level training or greater will obtain informed consent in one of three ways: 1) in-person, 2) electronically, or 3) via phone and mail correspondence, in accordance with patient preferences and availability, prior to participating.

**4.2a In-person Informed Consent Process:** Study staff will go through the informed consent discussion detailed above in a private room to protect patient confidentiality and answer any questions. Upon consent, study staff will maintain one copy of the informed consent form for study records, and participants will be instructed to maintain one copy for personal reference. Patients who would like more time to consider participation during in-clinic approach are able to take the forms home with them to review, and if interested, they may complete the consent process electronically (4.2b) or proceed to mail back the consent forms (see 4.2c).

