### **4.4 Registration**

Participants who provide informed consent will complete baseline study measures prior to registration. The research team will perform randomization procedures using computer generated randomization schema and assignments will be kept in concealed envelopes. We will complete the following registration procedures:

- Institutions will register eligible participants in the Clinical Trials Management System (CTMS) OnCore as required by DF/HCC SOP REGIST-101. When required by REGIST-101, registration must occur prior to the initiation of protocol-specific procedures or assessments.
- Registration requires a signed informed consent document and a completed eligibility checklist according to DF/HCC SOP REGIST-104.
- After randomization the research staff will inform the patients by phone, secure videoconferencing, or in-person of their study arm assignment.

If it is determined that a participant is ineligible or withdraws after signing consent and being enrolled on the study (i.e. unable to operate videoconferencing software, no longer interested in participating, etc.), their status on OnCore will be modified to “Off-Study” to reflect their status and a note will be added in the comments section. Additionally, study staff will add a Note to File as part of the regulatory documents of the study detailing any events of a lost participant.

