### **6.5 Stratification factors and their impact on design.** N/A

### **6.6 Early stopping rules, if appropriate.** N/A

**6.7 Definition of and allowance in design for unevaluable/ineligible participants.** No unevaluable and/or ineligible participants will be included in this study.

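### The videoconference test call decides eligibility but is not required before randomisation, so the plan allows avoidable post-randomisation exclusions

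*Combined protocol and SAP*

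**What the plan says.** Section 4.2 tells participants that "after signing the informed consent, they will complete a brief test call with a study staff member using the videoconferencing software", and attaches a consequence: "Subjects who are found to be unable to use the videoconferencing software during the brief test call will be considered ineligible for the study". The same section leaves out of the analysis any questionnaire answers from a person later judged ineligible.

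Section 5.6.3 refers back to 4.2 for this call but words it as a permission: "participants may test the software with a study staff member during a brief test call prior to the start of the intervention".

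Section 5.3 sets the trigger for randomisation: "Following completion of the baseline survey, participants will be randomized to the immediate start resiliency intervention group (IG) or waitlist control group (WG"). The test call is not mentioned there. Section 5.6.1 adds that "participants will not be registered on the study until they complete the baseline questionnaire and are randomized", and 5.1 likewise treats people who complete baseline and are randomised as enrolled.

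Section 4.4 provides for a participant who is "ineligible or withdraws after signing consent and being enrolled on the study (i.e. unable to operate videoconferencing software" being the first example given). Their registry status changes to off study, and a note to file is added. Section 6.7 states: "No unevaluable and/or ineligible participants will be included in this study".

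Three passages pull the other way. Section 3.0 promises to record how many people cannot take part because of the videoconference criterion. Section 5.1 lists inability to use the software among the reasons for ineligibility to be reported as proportions. Section 5.2.2 counts the eligibility rate among the feasibility measures.

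**The concern.** One call cannot be both a required step that settles eligibility and an optional rehearsal. Staff who follow 5.6.3 could skip it or hold it after allocation. A person who then cannot use the software has already been randomised, yet 4.2, 4.4 and 6.7 together treat them as someone who should not have been in the study.

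The primary aim is the feasibility of a programme delivered by videoconference. A randomised participant who cannot be reached by that route is a delivery failure. Such a person belongs in the denominators for attendance, completion and retention. If they are reclassified as ineligible, those rates may describe only the people for whom the technology worked. Their questionnaire data would also be lost from the exploratory T0–T1 comparison, which would then no longer include everyone randomised.

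**Working it through.** **1. Order of events.** The documents fix this sequence:
- consent (4.2);
- baseline survey, then randomisation (5.3);
- registration, only once baseline is complete and the participant is randomised (5.6.1).

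The call is placed after consent (4.2) and before the intervention (5.6.3). Both limits are met by a call held after randomisation. Section 4.4 requires a completed eligibility checklist for registration, but by 5.6.1 registration itself follows randomisation, so the checklist does not force the call to come first.

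**2. What happens to someone who fails after randomisation.** Under 4.4 they go off study. Under 4.2 their questionnaire answers are left out. Under 6.7 they are not included. Section 5.1 gives two answers on accrual: everyone who completes baseline and is randomised counts towards 72, but a person who takes part in no intervention visit does not.

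**3. Which measures are exposed.**
- Mean session participation and the proportion attending at least 6 of 8 sessions (6.2, 6.8.1): the denominator for such people is not stated.
- Retention (5.2.2): defined on enrollees, which would keep them in, but 6.7 would take them out.
- Change from T0 to T1 between arms (6.8.2): their data are lost under 4.2.
- Eligibility rate and reasons for ineligibility (5.1, 5.2.2): they are counted here.

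**4. The plan's own figure.** The plan gives no expected number of software failures. The only calculated feasibility figure is in 6.2: 90% power at n = 60 to show a mean 5.5 points above 75%, with SD 10 points and one-sided alpha 0.05. Using power = Φ(δ√n/SD − 1.645):
- n = 60: Φ(0.55 × 7.746 − 1.645) = Φ(2.615) = 99.6%, so the stated 90% is not reproduced;
- n = 30: Φ(0.55 × 5.477 − 1.645) = Φ(1.367) = 91.4%, or 90.3% by the noncentral t, which is close to it.

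That mismatch is a separate matter and nothing here depends on it. From 6.2 I use only the threshold (75%) and the design alternative (75 + 5.5 = 80.5%).

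**5. Illustration of size.** Assumptions: 72 randomised, k removed (not in the documents), removed people attended no sessions, and kept people average m. Without the removed people the mean is m. With them it is m × (72 − k)/72.

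| k removed | m = 80.5% | m = 85% | m = 90% |
|---|---|---|---|
| 1 | 79.4 | 83.8 | 88.8 |
| 2 | 78.3 | 82.6 | 87.5 |
| 4 | 76.0 | 80.3 | 85.0 |
| 5 | 74.9 | 79.1 | 83.8 |
| 8 | 71.6 | 75.6 | 80.0 |
| 12 | 67.1 | 70.8 | 75.0 |

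At m = 80.5% the threshold is crossed at k = 72 × (1 − 75/80.5) = 4.9, that is, five people. If instead 60 are kept and k are added back, the crossing is at 60 × (80.5/75 − 1) = 4.4, again five people, giving 80.5 × 60/65 = 74.3%. In that case the SD rises from 10 to about 23.5 points.

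**6. Timing by arm.** The latest time that 5.6.3 allows is near T0 for the immediate group. For the waitlist group it is after T1, which 5.6.1 puts up to about 12 weeks (± 2) after T0. A waitlist participant could therefore be removed after giving both T0 and T1 data. No section schedules a separate waitlist call at that point.

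**The case against.** The best defence is that the plan intends an early call. Section 5.6.3 defers to 4.2, which ties the call to consent. Both arms enrol and complete baseline together (5.4.3), and 5.6.2 uses the call as one occasion to explain hair sampling, with the first sample due at T0. This makes a call near baseline plausible. It does not require one, and 4.4 expressly expects software failures after enrolment.

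A reader might infer that technology failures disappear from the primary endpoint. The documents do not support that. Feasibility is a set of measures that includes eligibility rates and reasons for ineligibility, and 3.0, 5.1 and 5.2.2 ensure that these people are counted. What is exposed is narrower: the attendance, completion and retention rates, and the questionnaire data.

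A reader might also infer a bias between arms. The wording permits the timing to differ, but nothing schedules it to, and the between-arm comparisons are exploratory and unpowered.

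It is also fair to say that 4.4 changes a registry status and does not itself set an analysis denominator; 4.2 exempts questionnaire answers, not attendance. In addition, 5.1 and 6.2 already set aside people who attend no session for any reason, so some denominator loss would occur without the test-call rule. These points limit what can be attributed to the call. They also show that no section states the denominator for someone randomised and then found unable.

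Finally, a call before randomisation still leaves failures outside the attendance denominator. That is so, and it is why they need their own reported count.

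**Conclusion.** The point stands as a conflict between sections with a practical consequence. Sections 4.2 and 5.6.3 disagree on whether the call is required, no section makes it a condition of randomisation, and 4.2, 4.4 and 6.7 together permit a randomised participant to be declared ineligible for software inability and left out. These exclusions are avoidable. They could inflate attendance, completion and retention and thin the exploratory T0–T1 comparison.

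The size is unknown, because the documents give no failure rate. The five-removal crossing of the 75% threshold depends on kept participants averaging 80.5% and removed participants attending nothing. If kept participants averaged 90%, even 12 removals would bring the mean only down to 75.0%. The illustration shows that the rule can matter, not that it will. The documents do not establish that failures are concealed or that the arms would differ.

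**What to change.** - In 4.2, 4.4, 5.3 and 5.6.3, use the same rule: every participant completes the test call after consent and before randomisation.
- Count people who fail it as screening ineligibility due to technology, and report that number alongside attendance so that the reach of videoconference delivery is visible.
- Keep anyone found unable after randomisation in the randomised denominators as a non-attender, with the reason recorded, and retain their questionnaire data.
- Bring the two accrual statements in 5.1 and the exclusion in 6.7 into line with this.

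The call already exists, so the cost is its place in the sequence and wording in six sections. No visits, instruments or participants are added. This is a free improvement.
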